## Postoperatively:

- Must be admitted to the general pediatric floor postoperatively (versus intensive care unit)
- On POD #1 in the morning, patients in both groups will be visited by the research assistant. Patients in the VR arm will be offered the VR device for up to 30 minutes, and patients in the control arm will be offered an iPad for up to 30 minutes
- Number of hours since anesthesia end will be recorded
- Pain scores (FACES scale by the patient, FLACC scores by the research assistant) will be recorded immediately prior to intervention (T=0) and at end of intervention (T=30); FLACC score by research assistant will also be recorded at 10 minute mark (T=10)
- PCA use (in mcg or mg as appropriate) for previous hour prior to intervention (T=-60-0), during intervention (T=0-30), and one hour after intervention is complete (T=30-90) will be recorded; PCA use will be converted to morphine equivalents at time of data entry
- Total number of minutes of electronic device use will be recorded. The electronic device will be applied for a total of 30 minutes maximum, after which time the session will end
- On POD #1 in the afternoon, research assistant will return for patients in both groups, for another session up to 30 minutes. Data for both groups will be recorded as above

	If a patient declines to participate, the reason for declining will be asked for and recorded
	
 
Post-intervention:         
 
Patients and caregivers in the VR group will be given a survey regarding acceptance and effectiveness of the VR device in the postoperative period at approximately 48-72 hours
 
Patients and caregivers in both groups will be given a follow-up survey at approximately 48-72 hours and 7-10 days
 
Surveys will be conducted by phone, email or in person
 
 
 

Subject Population	Inclusion Criteria
key criteria for Inclusion	1. Subjects age 11 – 17
and Exclusion:	
 
Patients undergoing idiopathic scoliosis surgery on ERAS spine protocol (which includes postoperative PCA)
 
No contraindication to using an iPad or VR device
 

	Exclusion Criteria
	1. Patient/caregiver refusal
	2. Patients with developmental delay
	3. Patients with seizure disorder
	4. Non-English-speaking patients
	5. Patients with daily opioid use ≥ two weeks
	6. Patients with uncorrected visual or hearing impairment
	7. Patients admitted to pediatric intensive care unit on POD#1

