The anesthetic management of the patients will be left to the discretion of the anesthesia provider on the day of surgery but will follow the guiding principles of the pediatric spine ERAS protocol, which standardizes many aspects of anesthetic care including multimodal analgesia, fluid management, etc.

We are limiting our scope to POD#1 opioid usage. We do not hypothesize that VR use on POD#1 will affect opioid usage following hospital discharge.

Follow up: A follow up survey will be given using the Post Hospitalization Behavior Questionnaire for Ambulatory Surgery (PHBQ-AS) form at approximately 48-72 hours postop and 7-10 days postop via a phone call, email or in person from a member of the research team. The PHBQ-AS form is used to assess new onset behavior change associated with hospitalization, which has been documented in numerous studies. We believe that by assessing preoperative anxiety and preventing perioperative pain, which can lead to behavioral changes, the use of VR may decrease the chance of post hospitalization behavior change.

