## 4.3 Follow-up procedures (by visits)

There will be a follow-up survey using the PHBQ-AS form to assess new onset behavior change at approximately 48-72 hours postop and 7-10 days postop via a phone call from a member of the research team. These scores will be recorded and analyzed between both study groups.

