PHBQ-AS (Post Hospitalization Behavior Questionnaire for Ambulatory Surgery) – 11 items on a five-point scale (i.e., 1=Much less than before, 5=Much more than before). Total scores 11-55 (Jenkins et al, 2015)

These are all validated scoring systems in pediatric populations.

We will utilize the short STAI, as above.

Units of measurement for all variables of interest: Questionnaires and scales as above. In addition, hours since anesthesia end to start of visit (hours), PCA use (mcg or mg, at T=-60-0, 0-30, 30-90 min; converted to morphine equivalents at time of data entry), patient declines (0=Yes, 1=No), total duration of electronic device use (min), presence of dizziness (0=No, 1=Yes), presence of nausea (0=No, 1=Yes), anti-nausea medication requested during intervention (0=No, 1=Yes).

Patient and caregiver satisfaction: Qualitative satisfaction will be documented, divided into positive and negative comments.

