## **6.2** Secondary Outcomes

Our secondary outcomes and efficacy measures include: patient and caregiver satisfaction scores, presence of dizziness/nausea, time of discontinuation of VR/iPad if less than 30 minutes, and PHBQ-AS scores postoperatively at 48-72 hours and 7-10 days.

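### Only VR families get a device survey, in the window of the first PHBQ-AS and before the second: an avoidable possible source of differential reporting in a between-arm secondary outcome.

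*Combined protocol and SAP*

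**What the plan says.** The post-intervention part of the Protocol Synopsis lists two surveys.

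- The first is for one arm: "Patients and caregivers in the VR group will be given a survey regarding acceptance and effectiveness of the VR device", timed "in the postoperative period at approximately 48-72 hours".
- The second is for both arms: "Patients and caregivers in both groups will be given a follow-up survey at approximately 48-72 hours and 7-10 days".

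Section 3.1 (Follow up) identifies the second: "A follow up survey will be given using the Post Hospitalization Behavior Questionnaire for Ambulatory Surgery (PHBQ-AS) form". Section 5 describes that form as "11 items on a five-point scale", with totals from 11 to 55 and each item rated relative to before.

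Section 4.3 says of the PHBQ-AS: "These scores will be recorded and analyzed between both study groups". Section 6.2 lists "PHBQ-AS scores postoperatively at 48-72 hours and 7-10 days" among the secondary outcomes, and section 6.3 places the form under Aim 1.

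The VR-only survey appears in the synopsis alone. Sections 3.1 and 4.3 mention only the PHBQ-AS. No section schedules a matching survey for the iPad arm or states which form comes first at 48-72 hours.

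**The concern.** A randomized comparison of a subjective rating relies on both arms giving that rating under the same conditions. Here the written follow-up schedule differs by arm: VR families are asked about their device's effectiveness close to one PHBQ-AS and ahead of the other, and iPad families have no scheduled counterpart. The families doing the rating know which device they used.

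If answering the device survey changes how a family rates behaviour, the effect falls in one arm only. The analysis cannot separate it from an effect of VR, because having had the survey and being in the VR arm coincide completely. Section 6.3 makes the size of the estimates and their confidence intervals the main focus, and a reporting shift moves the estimate by its full amount.

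The arrangement also fits poorly with section 3.2, which withholds the device's identity at consent and says nothing to families about the other arm, in order to limit bias.

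**Working it through.** **Schedule by arm** (Protocol Synopsis, sections 3.1 and 4.3)

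| Contact | VR arm | iPad arm |
|---|---|---|
| POD 1, two sessions | Pain scores, PCA use | Pain scores, PCA use |
| About 48-72 h | Device survey and PHBQ-AS, order not stated | PHBQ-AS |
| 7-10 days | PHBQ-AS | PHBQ-AS |

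Three things follow.

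1. The primary outcomes are complete before any survey is given, so the survey cannot affect them.
2. At 48-72 hours the device survey may come before, alongside or after the PHBQ-AS. The synopsis lists it first, but a list of surveys is not an order of administration. Follow-up may also be by phone, email or in person.
3. At 7-10 days the order is fixed: the VR arm has already had the device survey. Taking 48-72 hours as days 2-3, the gap is between 7 − 3 = 4 and 10 − 2 = 8 days.

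**What can be said about size**

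The plan gives no PHBQ-AS standard deviation, effect size, power or numeric alpha, so there is no figure to reproduce. The rest is illustration. It assumes 10 completers per arm (the goal in section 3.3), a two-sided 5% level without the Bonferroni adjustment, and a two-sample t-test. Section 6.3 names that test for pain scores and opioid use only.

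- 95% CI half-width = t(0.975, 18 df) × √(2/10) = 2.101 × 0.447 = 0.94 SD.
- Suppose VR families rate 1 to 3 of the 11 items one category differently. The total moves 1 to 3 points. With an assumed SD of 3 to 6 points, the shift runs from 1/6 = 0.17 SD to 3/3 = 1.0 SD. The midpoints give 2/4.5 = 0.44 SD.
- With no true effect and a pure reporting shift of d SD in one arm, the noncentrality is d × √(10/2) = 2.236d. The exact noncentral t gives:

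| Assumed shift (SD) | Noncentrality | Chance of p < 0.05 |
|---|---|---|
| 0.25 | 0.56 | 8% |
| 0.50 | 1.12 | 19% |
| 0.75 | 1.68 | 36% |
| 1.00 | 2.24 | 56% |

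These rows show what a shift of a given size would do. They are not evidence that one would occur.

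**The case against.** The case for leaving the plan alone has real force.

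- **Order.** A reader might infer that VR families answer the device survey before the first PHBQ-AS. The documents do not say so; the PHBQ-AS could equally come first. For that time point the point is an unspecified order, not a demonstrated flaw.
- **Carry-over.** At 7-10 days the survey is some 4 to 8 days old, and the PHBQ-AS asks about behaviour, not the device. VR families have already had up to two sessions and know what they used. Nothing in the documents shows that one survey adds to that knowledge, or in which direction.
- **iPad satisfaction.** It is tempting to conclude that iPad families are never asked for an opinion. The satisfaction outcomes in the synopsis and sections 4.2, 5 and 6.2 name no arm. The objective in section 2.2 and the Aim 3 rationale in section 6.3 do point to VR, so the text is ambiguous. What can be said is that the only device survey with a stated schedule is for the VR arm.
- **Expected benefit.** Section 3.1 says only that VR may reduce behaviour change. It does not predict a reduction.
- **Standing of the outcome.** This is a 20-patient pilot. The PHBQ-AS is in neither stated objective and is absent from the secondary outcomes in section 4.2, though sections 6.2 and 6.3 include it.

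All of this limits the point. It does not remove it: the arms are still scheduled to rate a compared outcome under different conditions, for no reason the plan gives.

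**Conclusion.** The point stands as a modest one. The one-sided survey is an avoidable possible source of differential reporting in the PHBQ-AS comparison. The exposure is certain in sequence at 7-10 days and depends on an unstated order at 48-72 hours.

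The documents do not support saying that the PHBQ-AS result will be biased, that any bias would favour VR, or that it would be large. The 0.17 to 1.0 SD range rests wholly on assumed shifts and SDs, and its top end pairs the largest shift with the smallest SD. It should not be used to judge seriousness. The conclusion rests on the schedule, the subjective scale, families' knowledge of their device and the planned between-arm comparison.

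**What to change.** Make two changes, in both the synopsis and section 4.3:

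1. State that at the 48-72 hour contact the PHBQ-AS is completed before any device survey, however the contact is made.
2. Give the iPad arm the same acceptance and effectiveness questions at that contact, worded for its own device and without mention of the other arm, so that section 3.2 is respected.

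Both arms then complete the first PHBQ-AS with no prior device survey, and reach the second having answered equivalent questions. Device satisfaction can also be compared between arms. Families will still know which device they used; the change does not address that.

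Keep the VR survey at 48-72 hours. Holding it until after the 7-10 day PHBQ-AS would also protect that form, but it would expose data for the stated secondary objective, satisfaction with VR, to weaker recall and loss to follow-up.

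The cost is a few extra minutes of questions for about 10 iPad families, with no new contact. The synopsis time estimate (30 + 2 × 35 + 2 × 10 = 120 minutes) has no separate line for a device survey, so check that it still holds.

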Patient & caregiver satisfaction scores Presence of dizziness/nausea Time of discontinuation of VR if less than 30 minutes Safety and feasibility of VR in postsurgical populations has been Safety Evaluations proven in previous studies, some of which include specific spine surgery populations. Quantitative data analysis will be conducted under the supervision Statistical And Analytic of the biostatistician, using SAS or R. Plan All statistical estimates (e.g., means, medians, proportions, incidence rates, mean differences, correlations, etc.) will be tabulated along with corresponding confidence intervals (CIs). To avoid over-reliance on p-values, the magnitudes of estimates and the corresponding confidence intervals will be the primary focus of the analyses. The data collected during this study will be on hospital or School of Data and Safety Medicine computers with security features installed to protect the **Monitoring Plan** data. Data will be collected by a research assistant and will be monitored by members of the research study and other members of the Department of Anesthesiology research division. The Information Technology group within the Department of Anesthesiology provides secure data storage for the proposed study. Servers for the group are located in a locked office on the UNC campus. Study data on these servers is stored on SQL Server 2005s and backed up with nightly full backups. The web server is behind a firewall and only known and approved site users have access via ASP.NET forms authentication. This data management system meets or exceeds NIH security guidelines, safeguards participant data, and adheres to the Certificate of Confidentiality. Any adverse events will be collected in the data and reported to the PI and IRB as applicable. Based on the results, modifications in the postoperative management protocols at UNC will be considered as appropriate.

#### 1 BACKGROUND AND RATIONALE

#### 1.1 Introduction

Pain is a common complaint after surgery, and can be influenced by many factors, including anxiety. Distraction methods are commonly used with pediatric patients in the perioperative period to decrease patient and caregiver anxiety both before and during procedures. UNC and the Child Life team routinely use a variety of games and videos to assist in easing the pre- and postoperative experience for children and their families. Studies have shown that pain, anxiety and patient satisfaction are improved with the use of distraction methods as compared to treatment with medications alone. Studies have also compared these standard distraction methods to the use of virtual reality during minor procedures (dressing changes, IV lines, vaccines) and have shown that VR is an effective way to reduce anxiety, decrease pain, and improve patient satisfaction during these procedures. The majority of these studies have been done either during minor procedures or preoperatively as an introduction to the patient experience. In addition, studies show improvement in rehabilitation in certain populations. Little has been done to study VR in the postoperative period, particularly on the first postoperative day. Our group previously investigated VR use in the PACU following a broad range of pediatric surgeries last year, with favorable results. This study will focus on patients specifically undergoing pediatric scoliosis surgery, and will examine the use of VR on the first postoperative day. Scoliosis surgery is a common pediatric procedure that can be associated with significant postoperative pain. This study and data collection will be done at UNC Hospitals, including the Children's preoperative holding area and the Children's inpatient floors postoperatively.

## 1.2 Name and Description of Investigational Product or Intervention

The Applied VR is a lightweight mobile virtual reality headset with embedded software, creating an immersive experience. The Applied VR is specifically designed for medical use. Our group has received funding approval for a UNC Department of Anesthesiology grant to acquire 2 Applied VR units. (date of request 4/9/2020, date of approval 4/13/2020). These funds grant us the ability to purchase 2 Applied VR devices which includes the 12 month research subscription plan – software license, tech support, training, Pico G2 4K hardware (\$5000 total). We have successfully purchased these devices.

In comparison with the Oculus Go headsets used in our prior research study, the Applied VR carries several advantages including: lighter weight headsets; specific design for medical intervention with a HIPAA compliant platform; enhanced immersion including improved audio-visual synchronization, higher pixel count, 4K device (vs 3K device); improved infection control capability due to rubber straps instead of Velcro. Applied VR is manufactured by a leading virtual reality company that is defined as a wellness company; they have not achieved FDA approval given that they are considered as wellness devices. They have numerous studies demonstrating their software's impact on pain and anxiety. In addition, their headsets' more lightweight and comfortable design will be important in our pediatric patents.

In keeping with our group's accepted IRB application last year regarding postoperative virtual reality research, we plan to request a device determination from the IRB. We have determined that the device as used in this investigation meets the criteria for a non-significant risk (NSR) device.

## 1.3 Non-Clinical and Clinical Study Findings

By exploring non-pharmacologic methods of postoperative pain management in the form of virtual reality distraction, we hope to contribute to effective means of management for the common condition of postoperative pain. Postoperative risks associated with children are related to opioid administration and include over-sedation, respiratory depression, nausea and vomiting, and increased PACU stay. By providing a non-pharmacologic distraction method, we plan to minimize postoperative pain, opioid requirements, and lessen their possible adverse effects. As a result, children may receive fewer opioids, while benefiting from a positive hospital experience that is patient centered and age appropriate. There is a known small risk of motion sickness and nausea with the use of VR, but we believe that this risk will not be different in our study population, as evidenced by our previous VR study.

## 2 STUDY OBJECTIVES

The purpose of this study is to determine whether the use of virtual reality after pediatric idiopathic scoliosis surgery influences pain perception. We hypothesize that the use of virtual reality programs will provide superior distraction to standard electronic use and will result in improved pain scores and reduced opioid consumption after surgery.

#### 2.1 Primary Objective

To evaluate postoperative pain scores and postoperative opioid use in pediatric idiopathic scoliosis surgical patients using virtual reality as a method of immersive distraction compared with standard electronic use (iPad) postoperatively.

## 2.2 Secondary Objective

To evaluate patient satisfaction with use of virtual reality as a method of distraction.

## 3 INVESTIGATIONAL PLAN

#### 3.1 Study Design

This will be a randomized controlled pilot study comparing virtual reality to standard electronic use after pediatric idiopathic scoliosis surgery. Patients age 11-17 years old undergoing idiopathic scoliosis surgery will be included. Patients will be randomized to either the virtual reality or control (iPad) group. The randomization-and-concealment feature of REDCap data capture system will be utilized.

Subject eligibility will be verified by the research coordinator through chart review and patient questionnaire prior to enrollment in the study. The patients will be blinded to their study arm until they agree to be part of the study. Participants will be properly oriented to their respective device (VR or iPad) before surgery. While the use of VR may be new to the patients, VR is a very popular, trending and mainstream concept that is not likely to be unfamiliar to patients in the study age group. The patients will have the ability to stop using the VR device at any time if they choose.

## Study phases are as follows:

Screening/Consent/Baseline: Randomization and consent will be obtained preoperatively. A baseline anxiety score will be assessed on a self-report form (STAI short form). Patients in the VR arm will be oriented to the VR device before surgery. All patients will be oriented to the Wong-Baker FACES pain scale. Baseline pain scores will be obtained through the following method: FACES scale (patient reported) and FLACC score (measured by the trained research assistant). Baseline vital signs will be measured and recorded. The STAI, FACES, and FLACC scoring tools have all been used and previously validated in the pediatric population.

Intervention/Treatment: On postoperative day (POD) #1 in the morning, patients in both groups will be visited by the research assistant. Standardized scripts will be utilized by the research assistant for the entirety of the data collection. Patients in the VR arm will be offered the VR device for up to 30 minutes. Patients in the control arm will be offered an iPad for up to 30 minutes. After a total of 30 minutes maximum, the session will end. Routine data will be collected on pain scores and PCA use as below for both groups. On POD #1 in the afternoon, a research assistant will return for patients in both

groups, for another session of the respective electronic device for up to 30 minutes. If a patient declines to participate, the reason for declining will be asked for and recorded.

In the control arm of the study, the iPad will have a variety of vetted and screened games available. The content on the iPads will include puzzles, games, and movies that have been previously vetted and approved by the Child Life team, separate from this study, and are currently used as standard of care at UNC. The Child Life team is an integral part of pediatric postoperative recovery at UNC.

In the VR arm of the study, there will be selected programs to choose from. All of the content will be pleasant games or exploring programs, avoiding unpleasant and fast-moving settings such as fighting or racing. All of the content will be age appropriate, vetted and screened by the research team for violence or otherwise stressing scenarios, content requiring rapid eye motion or head movement, and content requiring more body movement than what can comfortably be done in a sitting or reclined position.

Both iPads and VR devices are interactive (regardless of fingers versus head movement) and this type of movement difference should not confound results. Our study aims to assess whether the VR immersive experience provides superior distraction to the standard of care (iPad use), thus by nature of the study design we are studying the difference in the two distinct types of experiences. Finger versus head movement use is inherent to the types of distraction and central to the distinct experiences. Similarly, there will be different apps between VR and iPad platforms by nature of the differences in platforms. Our goal is to examine whether an immersive experience is more beneficial than an iPad-based experience, rather than examine specific styles of games.

There will be no restriction to personal electronic use. Both groups will have access to their personal devices (cell phones, iPads) as is the standard of care. The study iPad will only be offered at specific times as designated twice a day on POD#1 for participants in the control group. Outside of the study windows, participants will not be provided with hospital iPads. Personal electronic devices including iPads are acceptable, as is the standard of care for patients to bring whatever they see fit into the hospital.

There will be a variety of popular games and apps, deemed to be content- and age-appropriate by the Child Life specialists. Program offerings will not vary by specific age or gender; our study will only include ages 11-17 and per discussion with Child Life the programs do not need to be subdivided to remain appropriate within this age range.

Standard of care for both groups will include PCA use as ordered by the surgical team as well as routine Child Life visits. The Child Life team is an integral part of pediatric postoperative recovery at UNC.

The following will be recorded: Number of hours since anesthesia end. Pain scores including FACES scale by the patient and FLACC scores by the research assistant will be recorded immediately prior to intervention (T=0) and at end of intervention (T=30); FLACC score will also be recorded at the 10 minute mark (T=10). PCA use, in mcg or mg as appropriate, for the hour prior to intervention (T=-60-0), during intervention (T=0-30), and one hour after intervention is complete (T=30-90) will be recorded. Total number of minutes of electronic device use will be recorded. PCA use will be converted to morphine equivalents at time of data entry.

The anesthetic management of the patients will be left to the discretion of the anesthesia provider on the day of surgery but will follow the guiding principles of the pediatric spine ERAS protocol, which standardizes many aspects of anesthetic care including multimodal analgesia, fluid management, etc.

We are limiting our scope to POD#1 opioid usage. We do not hypothesize that VR use on POD#1 will affect opioid usage following hospital discharge.

Follow up: A follow up survey will be given using the Post Hospitalization Behavior Questionnaire for Ambulatory Surgery (PHBQ-AS) form at approximately 48-72 hours postop and 7-10 days postop via a phone call, email or in person from a member of the research team. The PHBQ-AS form is used to assess new onset behavior change associated with hospitalization, which has been documented in numerous studies. We believe that by assessing preoperative anxiety and preventing perioperative pain, which can lead to behavioral changes, the use of VR may decrease the chance of post hospitalization behavior change.

